7.1.2. Trial Endpoints

Efficacy Endpoints

The efficacy endpoints are defined, as follows:

- Technical Success, defined as a combination of A0 ablations (complete tumor ablation with a surrounding 5 mm margin) and A1 ablations (complete tumor ablation with inadequate margins) based on contrast-enhanced MRI performed up to 7 days following the original ablation procedure.
- Technical Efficacy, defined as a combination of A0 ablations (complete tumor ablation with a surrounding 5 mm margin) and A1 ablations (complete tumor ablation with inadequate margins), based on contrast-enhanced MRI scans at 1 month (+/- 7 days) after the original ablation procedure.
- Local tumor progression (LTP), evaluated at every visit after the ablation of the target tumor(s). LTP describes the appearance of tumor foci at the edge of the ablation zone, after at least one contrast-enhanced follow-up MRI scan has documented adequate ablation and an absence of viable tissue in the target tumor and surrounding ablation margin by using imaging criteria.
- Secondary efficacy rate, defined as the percentage of tumors that have undergone successful repeat ablation following identification of local tumor progression at any time during study follow up.
- Progression-free survival, defined as length of time from the original ablation procedure until any type of disease progression (i.e. local or distant).
- Overall survival measured from the time of the original ablation procedure to the time of death or last follow-up if death has not occurred.

Confidential Page 26 of 61

Safety Endpoint

The safety endpoint is the rate of AEs and SAEs reported at each analysis and cumulatively throughout the entire study period.

Patient Reported Outcomes:

- Pain, as measured by Numeric Pain Rating Scale, before the ablation procedure (measured at Screening Visit), post ablation (within 7 days after ablation]), and at the 1-month follow-up visit.
- Quality of Life, as measured by EORTC QLQ-C30 and liver-specific EORTC QLQ-HCC18, before the ablation procedure (measured at Screening Visit), post ablation (within 7 days after ablation), and at each follow-up visit.

Health Economics:

 Health economics associated with the ablation procedure, including complete procedure time, ablation time, number of ablations, number and types of probes, change in probe position, number of computed tomography (CT) and ultrasound scans performed for probe and margin assessment, and length of hospital stay.

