8. STATISTICAL CONSIDERATIONS

8.1. Statistical Design, Method and Analysis Procedure

This is a single-arm, prospective, multicenter study designed to evaluate the efficacy and safety of the NeuWave Certus Microwave Ablation System in the treatment of Chinese patients

Confidential Page 40 of 61

who have a single HCC tumor up to 5 cm or who have a maximum of 3 HCC tumors of up to 3 cm per tumor.

Categorical variables will be summarized descriptively by frequencies and associated percentages. Continuous variables will be summarized descriptively by number of patients, mean, standard deviation, median, minimum, and maximum. Confidence intervals will also be provided for procedure-related variables. A detailed Statistical Analysis Plan (SAP) describing all planned analyses of data collected in this study will be finalized prior to any analysis of data.

There will be three analysis populations defined for summary of data collected in this study. The primary analysis of safety and effectiveness endpoints will be performed on the Full Analysis Set, defined as all patients who are enrolled in the study, are not part of the run-in phase, and have the NeuWave Microwave Ablation System used for ablation. A Per Protocol analysis set will be defined as all patients in the Full Analysis Set who have no major protocol deviations. Effectiveness analyses will be repeated for the Per Protocol Set. The Safety Set will include all patients who provide informed consent and have MW ablation attempted with the NeuWave system and includes run-in phase patients. The Safety Set will be used for summarization of safety endpoints only. Safety and effectiveness data collected on patients participating in the run-in phase may be summarized separately from the remaining patients. There will be at least one planned subgroup analysis based on whether or not patients have a repeat ablation in the first 30 days to correct a margin (A1 to A0). A summary of all efficacy endpoints as well as adverse event summaries will be provided for all patients who only have the initial, planned ablation procedure at Visit 2A. These summaries will also be provided for all patients who receive a repeat ablation in the first 30 days.

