The number and percentage of tumors achieving Technical Success will be summarized and a 95% confidence interval will be estimated. Technical Success will be evaluated based on the margin achieved after the first ablation and prior to any repeat ablations within the first 7 days.

A similar summary will be provided for Technical Efficacy. This endpoint will be based on the scan obtained at Visit 3 and will count as successes patients with A0 or A1 margins in that scan and who did not have an A2 margin since the Visit 2B scan. Additionally, if a patient received a repeat ablation for correcting a margin (to go from A1 to A0) within the first 30 days, this will also count as a success. Patients with repeat ablations to correct an A2 margin from Visit 2B to Visit 3 will not count as success for Technical Efficacy. The number and percentage of tumors with A0 and A1 margins will be presented as a subcategorization within each presentation of Technical Success and Technical Efficacy, as well as a summarization for the number and reasons for repeat ablations through Visit 3.

Local tumor progression rates at 1, 3, 6, 9, 12, 18, 24, 30, and 36 months will be estimated using the Kaplan-Meier method and 95% confidence intervals will be provided. Any repeat ablation required after Visit 3 (Month 1) will be identified as an instance of local tumor progression. A similar summary will be provided for the 36-month overall and progression-free survival rates.

Confidential Page 41 of 61

The number and percentage of patients experiencing AEs will be summarized at the preferred term level using the Society of Interventional Radiology (SIR) clinical practice guidelines for event categorization. A similar summary will also be provided for device-related AEs, procedure-related AEs, all SAEs, device-related SAEs, and procedure-related SAEs. Adverse event rates will also be estimated using cumulative patient years of exposure as the denominator as well as total number of patient ablations.

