8.4. Criterion of Acceptability/Unacceptability of Clinical Trial Result

No specific hypotheses are identified from which an acceptability criterion is determined. Evaluation of acceptable performance of the NeuWave Microwave Ablation System will be made through a comprehensive evaluation of all data collected in this trial and put in context with other available therapies for HCC.

Confidential Page 42 of 61

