The visit in the outputs should be derived based on the above visit schedule.

If a visit is performed "out of window" (i.e.between two visit windows), the visit should be analyzed as part of the the visit closest in terms of time or number of days as outlined by visit schedule, above. More details can be found in Table 1 of the protocol.

In case any retest performed within one visit, the visit in the outputs will be derived based on the above time windows. The visit with worst result will be used as the planned visit.

5 Levels of Significance

Given that no hypotheses are formally being tested in this study, no levels of significance are specified. Estimation of specified study endpoints will be performed using two-sided 95% confidence intervals (CI).

6 Analysis Sets

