8.1.8 Reporting Conventions

Quantitative variables will be summarized using descriptive statistics (by visit, when appropriate) and will consist of values for number of evaluable subjects, mean, standard deviation (SD), median,Q1, Q3, minimum, and maximum. In calculated statistics, mean, median, Q1, and Q3 will be displayed with one more digit than original data while the SD will be displayed with two more digits. Minimum and maximum will keep the same number of decimal digits as the original data.

Statistics	Format
Ν	ХХ
n	ХХ
Mean	X.X
SD	X.XX
Median	X.X
Q1, Q3	x.x, x.x
Min, Max	х, х
SE	x.xx
95% CI	[x.x, x.x]
P-Value	0.XXX
Missing	ХХ
Percentage	x.x%

Table 2 Presentation of Numbers

N = total number of subjects in the defined analysis set; n = total number of subjects in the specific category. If N is specified in the column heading, then any reference to the number of subjects in the body should be no larger than N.

Qualitative variables are summarized by counts and percentages and displayed by decreasing order of modalities if ordinal, and by alphabetical order otherwise. The number of subjects with missing data should be displayed when there is missing data (number of total evaluable subjects is less than number of total subjects in the defined analysis population set). The numerator is the total number of evaluable subjects in the specific category (n).

Unless otherwise stated, for percentages:

- One decimal digit should be given
- No percentage should be given for cells with 0 subjects
- Based on the number of subjects in the analysis set
- Counts of missing observations will not be included in the denominator, but will be presented.

8.1.9 Presentation of Tables/Listings/Figures:

The treatment label for all Tables, Listings, and Figures will be: NeuWave MW Ablation.

All data recorded during the trial will be presented in individual data listings on the SAF, unless otherwise specified (including scheduled and unscheduled data). All listings will be sorted by phase (main or run-in), site, subject, parameter, date, and time point (where applicable), if not otherwise stated. Further details are provided in the appropriate section for the analysis of the specific parameter.

Tables and figures will be presented by scheduled time point (where applicable), unless otherwise specified. By-visit tables and figures will be sorted by chronological scheduled time point (where applicable).

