8.4.1 Effectiveness Endpoint(s)

All effectiveness endpoints will be summarized for FAS and PPS. Subjects in run-in analysis set will be also summarized for technical success and technical efficacy endpoints.

The effectiveness endpoints are defined, as follows:

Technical Success

Technical Success, defined as a combination of A0 ablations (complete tumor ablation with a surrounding 5 mm margin) and A1 ablations (complete tumor ablation with inadequate margins) based on contrast-enhanced MRI performed at Visit 2B (up to 7 days following the original ablation procedure).

The number and percentage of tumors achieving Technical Success will be summarized. Percentage will be calculated relative to the total count of evaluable target tumor lesions at Visit 2B. A 95% confidence interval will be estimated using wald method. The number and percentage of tumors with A0, A1 and A2 margins will be presented as a sub-categorization :

Note: Ablation evaluation by Investigator is collected in "Ablation Zone Assessment" CRF page. A0: complete tumor ablation with adequate margin (surrounding 5 mm margin) A1: complete tumor ablation with inadequate margins

A2: Incomplete tumor ablation

A subject archieving technical success is defined as a subject with all tumors reaching A0 or A1 at Visit 2B. The number and percentage of subjects archieving Technical Success will be summaried as well. Percentage will be calculated relative to the total number of subjects in relavent analysis population (FAS or PPS). A 95% confidence interval will be estimated using wald method.

Number and percentages of reasons for A1 and A2 ablation categorization will be also summarized.

Technical Efficacy

Technical Efficacy, defined as a combination of A0 ablations (complete tumor ablation with a surrounding 5 mm margin) and A1 ablations (complete tumor ablation with inadequate margins), based on contrast-enhanced MRI scans at Visit 3 (1 month +/- 7 days) after the original ablation procedure.

Tumor-level analysis method is same as that of primary endpoint. The number and percentage of tumors achieving Technical Efficacy will be summarized and a 95% confidence interval will be estimated using Wald method. The number and percentage of tumors with A0 and A1 margins will be presented as a sub-categorization within each presentation of Technical Efficacy, as well as a summarization for the number and reasons for repeat ablations through Visit 3.

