8.5.1 Adverse Events

An AE is defined as any undesirable clinical occurrence in a patient. An AE does not necessarily have a causal relationship with the study medical device. AEs will be recorded since date of informed consent signature until 30 days after any ablation procedure except SAEs with 36 months follow-up period.

Adverse events will be summarized by System Organ Class (SOC) and Preferred Term (PT) and broken down further by maximum severity and relationship to study device or procedure. Number (n) and percentage (%) will be presented with the percentage calculated relative to the total number of subjects in the FAS/SAF as following:

- AE Overview (subgroup by initial only and repeat ablation, run-in analysis set and full analysis set, and total count of safety analysis set)
- AE by SOC and PT
- Procedure related AE by SOC and PT
- Study device related AE by SOC and PT
- Serious AE by SOC and PT
- Procedure related serious AE by SOC and PT
- Study device related serious AE by SOC and PT
- AE by SOC, PT, and maximum severity
- AE by SIR and PT
- AE listings will be prepared. Information including SIR, PT, relationship with device/procedure, seriousness, severity, AE start and end date, intervention/treatment taken, outcome of AEwill be presented.

AEs will be coded using MedDRA Version 19.0 or higher.

Procedure-related AE

A procedure-related AE is an adverse event related to the study procedure. The relationship with study procedure is recorded as "Unlikely related", "Possibly related", "Probably related", and "Causal relationship".

Device-related AE

A device-related AE is an adverse event related to the use of the study device. The relationship with study device is recorded as "Unlikely related", "Possibly related", "Probably related" and "Causal relationship". Events marked with missing relationship with study device is considered as device-related AE.

Serious Adverse Event (SAE)

A Serious Adverse Event is any AE that:

- Resulted in death: An AE that resulted in the patient's death.
- Life-threatening illness or injury: The patient was at imminent risk of dying at the time of the AE.
- Permanent Impairment: An AE that resulted in permanent impairment of a body function or permanent damage to a body structure.

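### SAP 8.5.1 gives the safety endpoint only counts and percentages, so the confidence intervals promised in SAP section 5 are not carried out for AE and SAE rates and no method is named

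*SAP*

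**What the plan says.** **The endpoint.** Protocol 7.1.2: "The safety endpoint is the rate of AEs and SAEs reported at each analysis and cumulatively throughout the entire study period". Efficacy and safety are the two halves of the key objective (Protocol 3.1).

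**The general promise.** SAP section 5: "Estimation of specified study endpoints will be performed using two-sided 95% confidence intervals (CI").

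**The safety tables.** SAP 8.5.1: "Number (n) and percentage (%) will be presented with the percentage calculated relative to the total number of subjects in the FAS/SAF". The list that follows covers all AEs, SAEs, device- and procedure-related events, severity and SIR class. No interval and no interval method appears in it. SAP 8.1.8 adds: "No percentage should be given for cells with 0 subjects".

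**The other endpoints.** SAP 8.4.1 names an interval repeatedly, for example for Technical Success: "A 95% confidence interval will be estimated using wald method". Wald is also named for Technical Efficacy, tumour-level local tumour progression and the secondary efficacy rate. Greenwood intervals are named for the Kaplan-Meier estimates, and quality-of-life changes get a 95% interval and a p value.

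**Related protocol text.** Protocol 8.1 plans two further sets of safety rates: "Adverse event rates will also be estimated using cumulative patient years of exposure as the denominator as well as total number of patient ablations". SAP 8.5.1 does not repeat them. Protocol 8.1 also says: "Confidence intervals will also be provided for procedure-related variables", without saying whether that covers adverse events.

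**The concern.** The study has no control arm, tests no hypothesis and is meant to support registration in China (Protocol 4.3, 8.2, 8.4). What such a study can say about harm is which rates its data exclude, and that needs an upper confidence limit. Tables are programmed from SAP 8.5.1, and as written that section yields n and % and, for a zero count, no percentage at all.

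If a programmer tried to honour SAP section 5 by borrowing a method from elsewhere in the SAP, the only one available for a simple proportion is Wald. That method breaks down for rare events, which is where the most important safety rows (device-related SAEs, deaths) are likely to fall.

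**Working it through.** **Sample size (reproduces the plan).** SAP section 7 wants at least 100 subjects with one year of data and allows 20% dropout: 100/(1 - 0.20) = 125. Adding 3 run-in patients at each of 4 sites gives 125 + 12 = 137. So the Safety Set is at most 137 and the Full Analysis Set at most 125, with 100 as the planned minimum followed to one year.

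**Upper limit with zero events.** Exact two-sided 95% upper limit = 1 - 0.025^(1/n):
- n=137: 2.66%
- n=125: 2.91%
- n=100: 3.62%

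**Wald against exact.** Wald is p ± 1.96·√(p(1-p)/n), with p the observed proportion. Clopper-Pearson limits are the 0.025 quantile of Beta(x, n-x+1) and the 0.975 quantile of Beta(x+1, n-x).

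| Observed | Wald 95% | Exact 95% |
|---|---|---|
| 0/137 | 0 to 0 (zero width) | 0 to 2.7% |
| 1/137 (0.7%) | -0.7% to 2.2% | 0.02% to 4.0% |
| 2/137 (1.5%) | -0.5% to 3.5% | 0.2% to 5.2% |
| 5/137 (3.6%) | 0.5% to 6.8% | 1.2% to 8.3% |

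At 0 events the Wald interval cannot contain any true rate above zero. If the true rate is 1% (assumed) and n=137, zero events occur with probability 0.99^137 = 0.252, so Wald coverage is at most 1 - 0.252, or about 75%, against a nominal 95%.

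**Chance of seeing no event at all**, (1-p)^n:

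| True rate p | n=137 | n=125 | n=100 |
|---|---|---|---|
| 0.5% (assumed) | 50% | 53% | 61% |
| 1% (assumed) | 25% | 28% | 37% |
| 2% (assumed) | 6% | 8% | 13% |
| 3.8% (cited) | 0.5% | 0.8% | 2.1% |

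The 3.8% is the major-complication rate printed in Protocol 4.1.1 and 10.2. The count given with it in 4.1.1, 8 of 221, is 3.6%. At 3.62% the chances are 0.6%, 1.0% and 2.5%, so the discrepancy changes nothing here.

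**Follow-up.** SAEs are collected to 36 months. A proportion over all 137 or 125 subjects counts early dropouts as if they had been observed throughout. The step from 2.7% (n=137) to 3.6% (n=100) shows how much the zero-event limit moves if only the planned one-year minimum is fully observed. The Protocol 8.1 rate per patient-year deals with this, but SAP 8.5.1 leaves it out.

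**The case against.** The strongest reply is that little is lost. SAP section 5 already promises intervals for endpoints, every analysis is descriptive (SAP 8.4), and descriptive AE tables are common practice. The zero-cell rule is a formatting convention, and anyone with n and N can compute the exact limit. Safety is also described by severity, relatedness, SIR class, listings, deaths, laboratory shifts, ECOG and pain. All of this is true, and it limits the point to a reporting gap with no data lost. It does not close the gap: section 5 names no method, SAP 8.5.1 applies none, and the nearest method to hand fails at low counts.

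Three stronger readings are tempting, and the documents do not support them:

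- **That the plan has no confidence limits for safety at all.** SAP section 5 covers endpoints in general, and the protocol's sentence on procedure-related variables is ambiguous in scope. The fault is that the promise is not carried out.
- **That acceptability will be judged from bare percentages.** Protocol 8.4 says otherwise: "Evaluation of acceptable performance of the NeuWave Microwave Ablation System will be made through a comprehensive evaluation of all data collected in this trial", set in the context of other HCC therapies. Protocol 8.1 also plans exposure-based rates. Nothing says that few or no events will be taken as proof of safety.
- **That the sample often misses relevant harm.** Neither document sets a relevant harm rate. The statement holds only for assumed rates of about 1% or less. At the cited 3.8%, seeing no event would be rare.

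**Conclusion.** The point holds as an internal inconsistency with a cheap remedy. SAP 8.5.1 does not deliver for the AE/SAE rate what SAP section 5 promises, and the SAP names no interval suited to low counts. With no events, the data would still allow true rates of up to 2.7% (n=137), 2.9% (n=125) or 3.6% (n=100). With 5/137, close to the cited major-complication rate, they would allow 1.2% to 8.3%.

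The limits assume independent subjects, each fully observed for the event. The 25% and 50% chances of seeing no event at n=137 rest on assumed true rates of 1% and 0.5%. For major complications near 3.8% the issue is imprecision, since a complete absence of events would be unlikely.

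It does not follow that Protocol 8.4 needs an acceptance rule based on the upper limit. Without a threshold such a rule would decide nothing, and the protocol deliberately sets no criterion.

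**What to change.** In SAP 8.5.1:

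1. Add two-sided exact (Clopper-Pearson) 95% intervals to the subject-level rates of any SAE, device-related SAE, procedure-related SAE, SIR class C-F events, and AE leading to death. Do this in the SAF and the FAS at each analysis. Individual preferred terms do not need it.
2. Exempt these rows from the zero-cell rule in SAP 8.1.8, so that a zero prints as 0/N, 0.0% [0.0, upper limit]; for example 0/137, 0.0% [0.0, 2.7].
3. For SAEs over 36 months, also carry over the rates per patient-year and per ablation from Protocol 8.1, because a simple proportion treats dropouts as fully followed.

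Protocol 8.4 can stay as it is. The cost is SAP wording, one extra column and the exposure-based rows the protocol already plans, with no additional patients or data. The small downside is that reported safety will look less favourable once the upper limits are visible.

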7.1.7. Safety Evaluation Method

1) Description of safety parameters

The safety parameters in this study are all AEs and SAEs for 30 days after any ablation procedure (original or additional); after 30 days post an ablation procedure through the end of the study, only SAEs will be reported and assessed. The safety endpoint is the rate of AEs and SAEs reported at each analysis and cumulatively throughout the entire study period.

2) Selection of method and time to evaluate, record, and analyze the safety parameters

Confidential Page 31 of 61

NeuWave Medical, Inc. NEU_2017_07

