14.4. Reporting Procedure, Contact Information

The investigator should provide the sufficient treatment for any AE of any patients, including the laboratory detection value with clinical significance whether or not it is related to this study.

From ablation of the patient, all AEs related to the patient's participation in this study should be followed up until the event is resolved, or if the event causes the permanent damage, it should be followed up until the event is stable and the clinical outcome is determined.

All AEs and SAEs will be reported for 30 days after any ablation procedure (original or additional); after 30 days post an ablation procedure through the end of the study, only SAEs will be reported. All AEs should be followed up, until the AE is resolved, stable or the study is completed.

The investigator should record the nature, severity, treatment and outcome of the AE or SAE, and determine whether it is related to the study device, or the ablation procedure specified in the study protocol. The investigator will report all AEs to the Sponsor via the study database EDC.

The investigator must submit any SAEs that occurred in the study and the device deficiencies that may cause an SAE, to the Sponsor and National Medical Products Administration (NMPA) (or designated person) immediately after being informed of the event. If required by the Sponsor, the further information should be provided.

All SAEs need to be followed up until the event is resolved (with or without sequela). When the event is not resolved or stable at the end of study, the medical monitor in this clinical study will decide whether it is necessary to collect the further follow-up information.

The investigator and Sponsor should report the SAEs which occurred in the study, and the device deficiencies that may cause an SAE, to the regulatory authorities at every level according to the requirements of laws and regulations.

For all SAEs and device deficiencies that may cause SAEs, the Sponsor should report to the Food and Drug Administration where the clinical study was filed and the competent department of health and Family Planning Commission within 5 work days after awareness. The Sponsor should also inform other clinical trial institutions/sites and investigators that participate in the trial and inform the Ethics Committees by their medical device clinical trial management departments in a timely manner.

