8.1.2 Study day

The onset day of AE is calculated from the date of first microwave ablation administrated to the date of the AE start date, as follows:

Onset Day = (date of event - date of first microwave ablation + 1) if date of event happens on or later than date of ablation.

Onset Day = (date of event – date of first microwave ablation) if date of event happens earlier than date of ablation.

Study Day will be calculated from the reference start date (date of first microwave ablation) and will be used to show start/stop day of assessments and events.

Study Day = (date of event – date of first microwave ablation + 1) if date of event happens on or later than date of ablation

Study Day = (date of event – date of first microwave ablation) if date of event happens earlier than date of ablation.

In the situation where the event date is partial or missing, the Onset Day/Study Day and any corresponding durations will appear missing.

If a date is partial, no imputation will be done except for adverse events (AEs). If the day of AE start is missing, the first day of the month is considered as the start date, unless the month is the same month as the month of ablation, in which case day will be set equal to the day of ablation. If month part is missing, the AE start date is imputed as the first day of the year, unless the same year of ablation, in which case day will be set equal to the day of ablation. If the day or month of AE end is missing, the day will be imputed as the end day of the month or the year, unless the same month or year as the day of ablation. If the imputed date happens later than death date, the date is replaced with death date.

Based on the protocol, there will be no imputation of missing data for any parameters or for early terminated patients.

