8.9 Subgroup Analysis

The subjects in Full Analysis Set are grouped by the number of ablation procedures:

• The initial only group contains all subjects who only receive the initial, planned ablation procedure at Visit 2A.

 The repeated group contains all subjects who receive a repeat ablation in the first 30 days

Subgroup analysis for Tumor type(primary HCC and recurrent HCC and other) for technical success and technical efficacy (analyzed for patient level and tumor level).

For subgroup analysis, the percentage and 95% CI will be provided by using forest plot.

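### The SAP's initial-only versus repeat-ablation AE percentages rest on unequal numbers of procedures and unequal AE windows, and both AE rates promised in the protocol are missing

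*SAP*

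**What the plan says.** **Collection window.** Protocol 7.1.7 assesses "all AEs and SAEs for 30 days after any ablation procedure (original or additional"), and only SAEs after that; Protocol 14.4 repeats this. SAP 8.5.1 agrees: "AEs will be recorded since date of informed consent signature until 30 days after any ablation procedure except SAEs with 36 months follow-up period".

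**Groups.** SAP 8.9 states: "The initial only group contains all subjects who only receive the initial, planned ablation procedure at Visit 2A". The repeated group is everyone re-ablated during the first 30 days. Protocol 8.1 asks for AE summaries under the same split.

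**Measure.** SAP 8.5.1 reports counts and percentages of subjects, "with the percentage calculated relative to the total number of subjects in the FAS/SAF". The first output on its list is "AE Overview (subgroup by initial only and repeat ablation, run-in analysis set and full analysis set", together with a Safety Set total.

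**Rates.** Protocol 8.1 adds AE rates with cumulative patient-years as the denominator, "as well as total number of patient ablations". Neither rate appears in the SAP text. Protocol 8.7 says that changes to the planned analyses will be specified in a protocol revision or in the SAP; no such change is stated.

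**Timing.** For events on or after the first ablation date, SAP 8.1.2 sets "Onset Day = (date of event - date of first microwave ablation + 1"). No planned variable measures time from a repeat ablation.

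**Status.** SAP 8.4 makes all analyses descriptive, without hypothesis tests.

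**The concern.** The two columns differ by construction in how many procedures a subject had and in how long non-serious AEs were recorded. A percentage of subjects absorbs both differences. The protocol planned two rates that would put the groups on a common scale, at least in part, and the SAP kept the split while leaving the rates out.

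Protocol 8.4 sets no acceptance criterion: performance is to be judged from all the data together. Descriptive safety tables are therefore the evidence in this registration study. A reader who takes the two columns as showing the relative risk of a repeat procedure would be reading a mixture of procedure count, window length and any true difference.

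**Working it through.** **The plan's own figure.** The plan states no AE rate or AE precision. Its one computed figure is the sample size: 100/(1 - 0.20) = 125, and 125 + 3 x 4 = 137. This reproduces.

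**Inputs.**
- Window: 30 days after each ablation for non-serious AEs, 36 months for SAEs (SAP 8.5.1).
- Repeat on day t = 1 to 30 (SAP 8.9).
- Low anchor for risk: 3.8% major complications, as printed in Protocol 4.1.1 for a cited series of 221 patients (8/221 is 3.6%). All other risks are assumptions.
- Share re-ablated: assumed. In that series 201 of 221 were complete after the first session, leaving 20/221 = 9.0%; 125 x 0.0905 = 11.3, about 11 subjects. Range shown: 6 to 25.

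**1. Window length.** Initial only: 30 days. Repeat: 30 + t = 31 to 60 days, a ratio of 1.03 to 2.0, before counting any later re-ablation for recurrence. This needs no assumption.

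**2. Procedural AEs.** With equal, independent risk p per procedure, one ablation gives p and two give 1-(1-p)^2.

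| p | Initial only | Repeat | Ratio |
|---|---|---|---|
| 3.8% | 3.8% | 7.5% | 1.96 |
| 10% | 10% | 19% | 1.90 |
| 20% | 20% | 36% | 1.80 |
| 40% | 40% | 64% | 1.60 |
| 60% | 60% | 84% | 1.40 |

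Per ablation, the ratio is 1.0 in every row.

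**3. Background non-serious AEs.** Take a constant rate giving 20% per 30 days. The repeat group shows 1 - 0.8^((30+t)/30): 20.6% at t = 1, 24.1% at t = 7, 28.4% at t = 15 and 36% at t = 30, against 20%. Per open-window day the ratio is 1.0. Per ablation it is (30+t)/60: 0.52, 0.62, 0.75 and 1.0 at the same days. The per-ablation rate alone therefore under-counts the repeat group when windows overlap, and both rates are needed.

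**4. Patient-time.** Full follow-up is 36 x 30.4375 = 1,096 days, of which non-serious AEs are collected on only 30 to 60 (more after a later re-ablation). With full follow-up as denominator in both groups, the ratio in step 3 returns to (30+t)/30. Only open-window days remove it.

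**5. How often the table would show the repeat group higher.** In 200,000 simulated trials of 125 subjects at p = 20%, its percentage was higher in 74%, 85% and 93% of trials with 6, 11 and 25 repeat subjects. With equal risk per patient the figure was 41% to 47%.

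**6. Denominator.** SAP 8.5.1 read literally divides by the whole FAS or SAF, even inside subgroups. With 11 repeat subjects of 125 and p = 20%, this prints 114 x 0.20/125 = 18.2% for initial only and 11 x 0.36/125 = 3.2% for repeat, the opposite direction.

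**The case against.** The strongest defence is that the display answers a different and legitimate question. Protocol 8.1 asks for the split. The percentage of patients with an AE after one ablation, or after an initial and a repeat ablation, is a valid description of burden, and the column labels disclose that one group had more procedures. Neither document says the table will show whether a repeat procedure is riskier than a first. The AE listings carry start dates and relationship to procedure, and ablation details are listed, so the information is not lost. All of this stands.

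Four stronger readings are tempting, and the documents do not support them:

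- A reader might infer that repeat ablation is bound to look more harmful. That needs independence between procedures and the subgroup's own denominator. Repeat ablation is at the physician's discretion (Protocol 7.2.2), and patients with a major complication, transfusion or drainage may be withdrawn (Protocol 7.1.5). The repeat group could therefore be enriched for uneventful first procedures, and the gap could shrink or reverse. Step 6 also shows that the literal denominator points the other way.
- A reader might infer a formal comparison. SAP 8.4 rules out testing.
- A reader might take this as the only subgroup safety display. The same bullet also shows run-in and full-analysis columns.
- A reader might apply the window difference to all AEs. SAEs are followed for 36 months in both groups.

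What the defence does not answer is the silent loss of both protocol rates. Nor do listings replace a summary: a reader would have to rebuild the per-procedure analysis by hand.

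**Conclusion.** The point holds as a defect of presentation and a departure from the protocol. The inequality in procedures and in the non-serious AE window follows from the SAP's definitions alone, and both promised rates are absent without a declared change. The planned percentages can describe burden; they cannot separate a riskier repeat procedure from a second procedure and a longer window.

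The size is conditional. Under equal, independent per-procedure risk the distortion is a ratio of 1.40 to 1.96 over p = 60% down to 3.8%. For background AEs it runs from about 1.03 (repeat on day 1) to 1.8 (day 30) at 20% per 30 days. Only the 3.8% comes from the documents; the other risks and the repeat shares are assumptions, and the direction is not guaranteed. At the 1-month interim the window gap may be partly cut off; it is complete at 12 months and at the end.

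This should be corrected. It does not affect the effectiveness endpoints or the whole-set count of subjects with AEs.

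**What to change.** In SAP 8.5.1, with supporting derivations in 8.1.2:

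1. Restore both rates from Protocol 8.1: AEs per ablation and AEs per patient-time. For non-serious AEs, limit patient-time to days when the AE window is open.
2. Add a table of the percentage of procedures followed within 30 days by at least one AE, related AE and SAE, by ablation number. Include repeat ablations after day 30: subjects first re-ablated then fit neither group in SAP 8.9, although their AE window reopens.
3. State a rule for AEs in overlapping windows. For example, censor the first procedure's window at the repeat ablation and give rates per open-window day. Assigning every AE to the most recent ablation, without that adjustment, would cut the first window short and understate first-procedure risk.
4. Use each subgroup's own N as the denominator for subgroup percentages.
5. Keep the initial-only and repeat subject percentages, labelled as a description of patient burden.

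If the sponsor prefers to drop either rate, the SAP should say so and why.

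The cost is SAP wording, a few derived variables and one table. Ablation and AE dates are already collected.
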